3.8 Training

The aim of the T2DEx training is to equip clinicians and practice staff with sufficient understanding of Fresh Start's objectives and operations to deliver it autonomously at their respective sites. The training will be divided **into three sessions lasting approximately 1.5 hours each**. These sessions will be led by a member of the ICHP team or a clinical implementation role funded through NHSX.

Training sessions will be run via Microsoft Teams using training slide decks that has been created by ICHP. The slide decks form part of the virtual resource pack hosted in Teams, which includes all materials required for Fresh Start delivery. The trainer will walk the attendees through the slide deck, allowing time for questions during the session and at the end. Attendees will receive a feedback form at the end of each session to record their feedback on the training. After each session the trainer will share a copy of the deck with all attendees and invite the attendees to send any questions.

- **The first session** will provide an introduction to the Fresh Start objectives and an overview of all the Fresh Start components. Staff tasked with delivering Fresh Start should attend the full session. This will likely include PNs (practice nurses), healthcare assistants (HCAs), and administrative staff. General practitioners (GPs) or advanced nurse practitioners (ANPs) involved with running the VGCs should also attend the full session. It is recommended that other staff attend the first 15 minutes of this session if they will assume responsibility for any Fresh Start components when their colleagues are absent or on annual leave. At the end of the first session, attendees will be shown the virtual resource pack in Teams. The aim is to show the attendees a summary of the resource pack materials and the location of the materials they will require for their role in Fresh Start. All attendees should be given access to

the resource pack to review and the opportunity to contact the training team with questions.

- **The second session** will cover the search, outreach, qualification and booking, onboarding and Huma Clinician Dashboard monitoring components of Fresh Start . Staff responsible for these components should attend the full session. This will likely include HCAs and administrative staff. A representative from the Huma Customer Success team will join the session to demonstrate the Huma sign-up process and answer questions on the application and dashboard functionality. At the end of the second session attendees will be shown the resource pack folders relevant to the Fresh Start components covered in the session. All attendees should be given access to the demo versions of the Huma App and the Huma Clinician Dashboard to test in their own time. Attendees may have questions about the app and dashboard, which might require an additional session with Huma. It is recommended that short role-play sessions on onboarding and Clinician Dashboard monitoring are held before Fresh Start is formally launched.
- **The third session** will cover the VGC elements of Fresh Start; before, during and after. Staff responsible for these components should attend the full session. This will likely include HCAs, administrative staff, PNs, GPs or ANPs. A clinician familiar with the VGC content can join the session to deliver the 'during' section. At the end of the second session attendees will be shown the resource pack folders relevant to the Fresh Start components covered in the session. It is recommended that staff involved with delivering VGC session run a practice session to test Microsoft Teams and the content and structure of the session.

3.9 Follow-up

Patient's will be assessed at follow-up appointment with their primary care practice at month 6 (i.e., 3 months after completing the programme). Outcome measures recorded at this appointment will include:

- HbA1c
- Blood pressure
- Blood glucose
- Lipids
- Diabetes Distress Scale (DDS)

3.10 Study timeline

The below table gives a high-level overview of the study timeline.

Month	1	2	3	4	5	6	7	8	9
Recruit GP practices and train clinicians									
Recruit participants									
Deliver the intervention									

Follow-up period								
Interviews with patients and HCPs								
Analysis and write-up								

3.11 Data analysis

The research team will not have access to any personal or identifiable patient data as part of the project. Data will be de-identified before being transferred to WSIC's de-identified data (DID) environment and made available to approved researchers. Any data extracted from the secure environment after analysis by the research team will be at an aggregate level only.

All outcomes will be reported using descriptive statistics with tables and graphical presentations of findings. Continuous variables will be presented as means and standard deviations if normally distributed, and as medians and inter-quartile ranges for skewed data, whilst categorical variables will be presented as frequencies and percentages.

To assess the pre-test/post-test change on clinical outcomes the appropriate generalized mixed model approach will be used to account for repeated measurements and clustering of GP practices and including important covariates in the model.

To create a matched control group from NWL's WSIC database, a 1:1 propensity score matching (PSM) analysis will be performed using age, gender, risk category, geographical proximity and social deprivation index as matching variables. R statistical software will be used for estimating PS by logistic regression and for balance and sensitivity checks.

Comparisons with the control group for clinical outcomes will be exploratory and differences with 95% CI will be reported using the appropriate generalized mixed model.

Interviews conducted with participants and healthcare professionals will be analysed using NVivo, where responses will undergo thematic analysis using an inductive approach to derive key themes.

3.12 Data privacy and security

The research team will not have access to any personal or identifiable patient data as part of the project. Data will be de-identified before being transferred to WSIC's de-identified data (DID) environment and made available to approved researchers. Any data extracted from the secure environment after analysis by the research team will be at an aggregate level only.

A single WSIC analyst who is responsible for flagging patients in the matched control group will have access to the personal identifiable data (PID) environment. This WSIC analyst has

a substantive contract with the data controller and is authorised to execute the flagging in the PID.

The WSIC dataset is a PID hosted by UKCloud in a secure cloud-based environment, which is ISO27017 certified. This is an Identifiable data set which supports clinicians and health care professionals to provide joined-up care, decision-support and workflow automation. This information feeds into a wide range of bespoke assets for example clinical facing WSIC dashboards and the Health Information Exchange (HIE) for use by clinicians, and the Care Information Exchange (CIE) and coordinate my care for use by citizens.

Discover Dataset is de-identified dataset hosted in a secure Azure environment and to be hosted by IBM in a new Trusted Research Environment (TRE). This depersonalised data set is for quality improvement planning and research, it is controlled by NWL data controllers, and access to it is mediated by the NWL Data Access Committee. It is accessible via Discover-NOW Health Data Research Hub for Real World Evidence through their data scientists specialists hosted by Imperial College Health Partners (ICHP) and IG committee-approved analysts to conduct research within the safe environment.

Data collected on the Huma platform is hosted in the UK by Google Cloud Platform (GCP) who manage all physical servers, resources and networking hardware to enable all business logic and higher-level services. All communications are secured by TLS. Huma follows NIST approved encryption techniques for encrypting data-at-rest. Huma's cloud provider provides Key Management Services (KMS) for data storage services using an encryption key. Key rotation is performed. Huma practises the concept of least-privileged permissions for services. Huma also conforms to the following accreditations and standards:

- NHS Data Security and Protection Toolkit certification (organisational code: YGMA8)
- ISO13485 Certified Quality Management System with robust Risk Management Plan that includes Data Security & Protection, Business Continuity, Disaster Recovery, & implementation of Corrective & Preventive Actions

4. Recruitment

4.1 Recruitment to Fresh Start

Participants will include patients from participating primary care practices in NWL with 'high risk' and 'very high risk' of developing complications from T2DM. Risk stratification has been defined by guidance for primary care from NHS England and NHS Improvement (London) entitled *Primary Care: Identification, risk stratification and interventions for patients at an increased risk*. EPR searches have been constructed based on this risk stratification.

Selected patients will then be invited to participate in the program, with those who accept being onboarded (see Section 3.7 for more detail).

4.2 Recruitment for interviews – people with type 2 diabetes (x10) and HCPs (x10)

A total of 10 people with type 2 diabetes and 10 HCPs will be recruited to participate in interviews to assess the acceptability of Fresh Start to HCPs. Potential interviewees will be sent an email invitation to take. Those that express an interest in taking part will be emailed a participant information sheet and consent form by a member of the research team. Interviews will be carried out via Microsoft Teams and the duration of each interview will be approximately 45 minutes.

Participants will have a choice on the consent form to allow the researchers to audio-record the interview for the sole purpose of analysing the transcript in NVivo. All recordings will be deleted once transcription has been completed using a service such as PageSix. Alternatively, participants who do not wish to be audio recorded can still take part, the researcher will be responsible for capturing written notes during the session.

Participants in the interviews to assess Fresh Start's acceptability will be remunerated. Public participants (i.e., people with type 2 diabetes) will be paid £30 per hour for this online engagement (£25 per hour for their involvement plus an additional £5 to cover for WiFi/electricity). This is as per latest INVOLVE guidelines on patient and public involvement in research activity. All clinicians will be paid £100 per hour for their involvement.

4.3 Inclusion criteria

- Patients over the age of 18 with the capacity to give consent
- Patients with 'high risk' OR 'very high risk' T2DM as defined by:
- **Very high risk - T2DM with existing ASCVD OR T2DM without ASCVD but with any 3 of the following:**
 - HbA1c >58 mmol/mol
 - SBP >140 mm Hg
 - Non-HDL >3.35 mmol/L or LDL-C >2.5 mmol/L
 - Nephropathy (eGFR <45 ml/min, or Urine ACR >3 mg/mol)
 - Retinopathy
 - Neuropathy (including moderate/high risk feet, previous foot ulceration and erectile dysfunction)
 - Currently smoking
- **High risk - T2DM without ASCVD but with any 2 of the following:**
 - HbA1c > 58 mmol/mol
 - SBP >140 mm Hg
 - Non-HDL >3.35 mmol/L or LDL-C >2.5 mmol/L
 - Nephropathy: eGFR <45 ml/min or Urine ACR >3 mg/mol
 - Retinopathy

- Neuropathy (including moderate/high risk feet, previous foot ulceration and erectile dysfunction)
- Currently smoking
- Black, Asian and minority ethic (BAME) status

4.4 Exclusion criteria

- Participants too ill to participate in the study (i.e., presence of a life-threatening condition, expected survival less than 3 months, clinically unstable)
- Participants who have previously participated in efforts that have informed the design of this research.
- Participant without access to a smartphone.
- Non-English language (the remote monitoring technology currently does not support additional languages).
- Visual disability (the remote monitoring technology currently does not natively support visual assistance).
- Active severe mental illness (SMI).
- Alcohol / drug abuse.
- Severe frailty (identified via the Electronic Frailty Index – eFI).
- Housebound / living in nursing home.
- Currently on the REWIND Programme (a NWL total diet replacement programme for patients with type 2 diabetes).

4.5 Withdrawal criteria

Subjects may be withdrawn from the study at the discretion of the investigator team due to a safety concern or if judged non-compliant with trial procedures. Reasons for withdrawals and discontinuation of any subject from the protocol will be recorded by the investigator team.

A subject must be withdrawn from treatment if one of the following applies:

- Subject chooses to withdraw from the study (at any time)
- Major violation of the study protocol
- Other circumstances that would endanger the health of the subject if he/she were to continue his/her participation in the trial

5. Adverse events

5.1 Definitions

Adverse Event (AE): any untoward medical occurrence in a patient or clinical study subject.

Serious Adverse Event (SAE): any untoward and unexpected medical occurrence or effect that:

- **Results in death**

- **Is life-threatening** – refers to an event in which the subject was at risk of death at the time of the event; it does not refer to an event which hypothetically might have caused death if it were more severe
- **Requires hospitalisation, or prolongation of existing inpatients' hospitalisation**
- **Results in persistent or significant disability or incapacity**
- **Is a congenital anomaly or birth defect**

Medical judgement should be exercised in deciding whether an AE is serious in other situations. Important AEs that are not immediately life-threatening or do not result in death or hospitalisation but may jeopardise the subject or may require intervention to prevent one of the other outcomes listed in the definition above, should also be considered serious.

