5.2 Reporting procedures

All adverse events should be reported. Depending on the nature of the event the reporting procedures below should be followed. Any questions concerning adverse event reporting should be directed to the Chief Investigator in the first instance.

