5.2.1 Non serious AEs

All such events, whether expected or not, should be recorded- it should be specified if only some non-serious AEs will be recorded, any reporting should be consistent with the purpose of trial end points.

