5.2.2 Serious AEs

An SAE form should be completed and emailed to the Chief Investigator within 24 hours. However, hospitalisations for elective treatment of a pre-existing condition do not need reporting as SAEs.

All SAEs should be reported to the Bromley Research Ethics Committee ([contact]) where in the opinion of the Chief Investigator, the event was:

- 'related', ie resulted from the administration of any of the research procedures; and
- 'unexpected', i.e., an event that is not listed in the protocol as an expected occurrence

Reports of related and unexpected SAEs should be submitted within 15 days of the Chief Investigator becoming aware of the event, using the NRES SAE form for non-IMP studies. The Chief Investigator must also notify the Sponsor of all SAEs.

Local investigators should report any SAEs as required by their Local Research Ethics Committee, Sponsor and/or Research & Development Office.

Contact details for reporting SAEs

[contact]

CI email (and contact details below)

Please send SAE forms to: [contact] and Cc [contact]

[contact] (Mon to Fri 09.00 – 17.00)

6. Regulatory issues

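### Protocol 5.1 makes being unexpected part of the SAE definition, 5.2.2 treats it as a later step against a list that is not given, and a serious event a site judges expected may have no expedited route

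*Protocol*

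**What the plan says.** Protocol 5.1 gives two definitions. An adverse event carries no expectedness condition: "Adverse Event (AE): any untoward medical occurrence in a patient or clinical study subject". A serious adverse event does: it is "any untoward and unexpected medical occurrence or effect that" meets one of the listed outcomes, among them death and "Requires hospitalisation, or prolongation of existing inpatients' hospitalisation". A closing paragraph adds that "Medical judgement should be exercised in deciding whether an AE is serious in other situations".

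Protocol 5.2 opens with a general rule, "All adverse events should be reported", and sends the reader to the procedures beneath it. Section 5.2.1 covers non-serious events: "All such events, whether expected or not, should be recorded". Section 5.2.2 covers SAEs. It requires a form to reach the Chief Investigator within 24 hours, with planned admissions for a condition the patient already had exempted. It requires the Sponsor to be told of every SAE, and a report to the ethics committee within 15 days for those SAEs that the Chief Investigator considers both related and unexpected. Unexpected is explained there as "an event that is not listed in the protocol as an expected occurrence".

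**The concern.** Seriousness describes the outcome of an event; expectedness describes whether it was foreseen. Section 5.1 merges the two, while 5.2.2 treats them as separate steps. Every expedited duty in Section 5 attaches to SAEs, so an event kept out of the SAE definition escapes all of them.

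Participants have existing atherosclerotic cardiovascular disease or several risk factors (Protocol 4.3). A site could reasonably regard a cardiovascular admission in such a patient as expected and, following 5.1 to the letter, not complete a form. The Chief Investigator would then have no prompt to consider whether the event was related to Fresh Start. Safety of the service is a stated secondary objective (Protocol Section 2).

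**Working it through.** No arithmetic applies: the documents give no expected rate of deaths or admissions and no figure that depends on this definition. The check is to follow one event through Section 5, namely a death or non-elective admission that the site considers expected.

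| Step | Text | Result for this event |
|---|---|---|
| Is it an AE? | 5.1, AE definition | Yes; expectedness is not a condition |
| Is it an SAE? | 5.1, SAE definition | No, on a literal reading |
| Does the medical-judgement paragraph bring it back? | 5.1, closing paragraph | No; it extends seriousness to other important events that did not cause death or admission |
| Is it a non-serious AE under 5.2.1? | 5.2.1 | Not naturally; its outcome is on the serious list |
| 24-hour form to the Chief Investigator? | 5.2.2 | Not required; SAEs only |
| Sponsor notification? | 5.2.2 | Not required; SAEs only |
| Ethics committee assessment? | 5.2.2 | Not reached; starts from SAEs |
| Does the general rule apply? | 5.2 | Yes, but with no time limit and no matching procedure beneath it |

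The outcome depends on what *unexpected* means in 5.1, which 5.1 does not say. There are three possibilities.

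1. **Site judgement.** The event drops out as in the table. The site settles expectedness before the Chief Investigator sees the event, although 5.2.2 gives that decision to the Chief Investigator.
2. **The 5.2.2 meaning carried back to 5.1, with no list.** The protocol text contains no list of expected events, and its table of contents shows no section or appendix for one. On this meaning no event is expected, so nothing is lost at 5.1. The expectedness test in 5.2.2 is then also passed by every event, and relatedness alone decides what goes to the ethics committee.
3. **The 5.2.2 meaning carried back, with a list added later.** Every event on the list would stop being an SAE. Supplying the list without correcting 5.1 would make the exclusion real.

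If the word means the same in both places, the test in 5.2.2 has no work to do, because every SAE has already passed it. Section 5.2.2 makes sense only if an SAE can be expected, and 5.1 says it cannot.

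Finally, the comparative safety outcomes. Protocol 3.6 and SAP 6.3.1 and 7.6.1 count deaths, emergency department admissions and hospital admissions in both groups from patient records and WSIC, whatever anyone judged expected. These counts do not pass through the SAE definition.

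**The case against.** The strongest reply is the second possibility above. The only meaning the protocol gives to *unexpected* is absence from a list, and with no list nothing is expected. On that view every untoward death or non-elective admission is an SAE, and 5.1 contains only a stray phrase. The surrounding text supports broad capture as the intention: the elective exemption would be largely unnecessary if expected admissions were already outside, and 5.2.2 applies expectedness only to the Chief Investigator's decision on ethics reporting. This shows what was probably meant. It does not settle what a site will do, because 5.1 does not refer to the list or to 5.2.2. What stands is that the exclusion is one reading of an undefined word.

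A reader might infer that the protocol is stricter for minor events than for serious ones, since "All such events, whether expected or not, should be recorded" appears only for non-serious events. The comparison is not like for like: 5.2.1 concerns recording and 5.2.2 expedited reporting. A serious event denied SAE status is still an AE under the general rule. Section 5.2.1 also retains what looks like unedited template guidance, so its wording is weak evidence of a deliberate contrast.

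A reader might also infer that a large share of serious events would be called expected. No figure supports that. Enrolment covers high-risk as well as very-high-risk patients, and Protocol 4.4 excludes life-threatening conditions, short expected survival, clinical instability and severe frailty, which narrows the deaths a site could call expected.

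**Conclusion.** Sections 5.1 and 5.2.2 are inconsistent and should be reconciled. As written, a serious event that a site judges expected has no stated expedited route, and neither the medical-judgement paragraph nor the general reporting rule provides one. The conclusion rests on a literal reading of 5.1 and on sites using their own notion of expectedness, which the text leaves open.

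It would go too far to say that expected deaths and admissions definitely fall outside SAE reporting, or that they go unrecorded. The first depends on undefined judgement, and the general rule contradicts the second. Nor is there any basis for saying that the safety results are compromised: the counts and the composite comparison in SAP 7.6.1 are unaffected. Those counts are, however, later extractions analysed on de-identified data (Protocol 3.11), so they do not replace prompt review of whether an individual event was related to the service. The gap is in timely reporting and causality review, and its size cannot be calculated from the documents.

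**What to change.** Three wording changes to the protocol:

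- In 5.1, delete *and unexpected* from the SAE definition, so that seriousness rests on the listed outcomes alone.
- In 5.2.2, keep relatedness and expectedness as the test for reporting to the ethics committee, and nowhere else.
- In 5.2.2, either supply the list of expected events or state that no events are pre-specified as expected. Simply removing the reference to the list would leave *unexpected* undefined at the one step where it is still needed.

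The cost is a short protocol amendment and some additional SAE forms for sites and the Chief Investigator. No change to the SAP, the data extraction or the sample size follows.
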